8.1.1.2 EDSS Confidence Scale

For each EDSS score that is obtained retrospectively from medical charts and at the time of Study Visit 1, the evaluating physician will be asked to complete the EDSS Confidence Scale which is a single question indicating their confidence in that score's accuracy. This will be based on a non-validated 4-point Likert scale where 0 = not at all confident and 3 = highly confident.

8.1.1.3 Bedridden Status

A patient's status as being bedridden will be determined by EDSS scores of 8.0 or higher ("essentially restricted to bed or chair or perambulated in wheelchair but may be out of bed itself much of the day"), if available, or by clinical descriptions in medical records.

8.1.1.4 Subsequent Disease Modifying Drugs and Treatment Decisions

Details of subsequent DMDs, including physician questions on treatment decisions will be captured in the eCRF, based on chart review to determine the time, type, and reason for the first sequential treatment after the first course of Cladribine Tablets and the categorization of the second sequential treatment (categorized by platform injectable therapies, monoclonal antibody disease modifying treatments, oral disease modifying treatments, other, and unknown treatments).

8.1.1.5 First Use of Ambulatory Device

The date of first use of ambulatory device will be determined through retrospective chart review, based on an EDSS score of 6.0 or higher (score of 6.0 is defined as “intermittent or unilateral constant assistance [cane, crutch, brace] required to walk about 100 meters with or without resting”) or clinical descriptions if EDSS scores are not available.

8.1.1.6 First Use of Wheelchair

The date of first use of a wheelchair will be determined through retrospective chart review, based on an EDSS score of 7.0 or higher (score of 7.0 is defined as unable to walk beyond approximately 5 meters even with aid, essentially restricted to wheelchair; wheels self in standard wheelchair and transfers alone; up and about in wheelchair some 12 hours a day) or clinical descriptions if EDSS scores are not available.

8.1.1.7 Relapse Count

The following information on relapses will be recorded on the relapse module of the eCRF, if available: the number of relapses from end of parent study to Study Visit 1; relapse onset date and stabilization/resolution date; estimated relapse duration; maximal EDSS at time of relapse (if known); major systems affected; treatment required for relapse; patient hospitalization for relapse; outcome of relapse (i.e. increase in disability). A relapse will be defined as patient-reported symptoms and objectively observed signs typical of an acute inflammatory demyelinating event in the CNS, developing acutely or sub-acutely, with duration of at least 24 hours, in the absence of fever or infection (Thompson, 2018).

8.1.1.8 Conversion to Clinically Definite Multiple Sclerosis (ORACLE MS Participants Only)

Conversion to CDMS will be determined according to the McDonald 2017 criteria (Thompson, 2018; Table 2). For more details please see Appendix 6 2017 Mc Donald Criteria (From Thompson, 2018)).

Table 2 The 2017 McDonald criteria for diagnosis of Multiple Sclerosis in patients with an attack at onset

Clinical Presentation	Additional Data Needed to Make MS Diagnosis

 • ≥ 2 attacks and objective clinical evidence of ≥ 2 lesions • ≥ 2 attacks and objective clinical evidence of 1 lesion with historical evidence of prior attack involving lesion in different location 	
None. Dissemination in space (DIS) and dissemination in time (DIT) have been met.

 • ≥ 2 attacks and objective clinical evidence of 1 lesion 	
One of these criteria:
 
 • DIS: additional clinical attack implicating different CNS site • DIS: ≥ 1 symptomatic or asymptomatic MS-typical T2 lesions in ≥ 2 areas of CNS: periventricular, juxtacortical/cortical, infratentorial or spinal cord

 • 1 attack and objective clinical evidence of ≥ 2 lesions 	
One of these criteria:
 
 • DIT: additional clinical attack • DIT: simultaneous presence of both enhancing and non-enhancing symptomatic or asymptomatic MS-typical MRI lesions • DIT: new T2 or enhancing MRI lesion compared to baseline scan (without regard to timing of baseline scan) • Cerebrospinal fluid (CSF)-specific (i.e. not in serum) oligoclonal bands

 • 1 attack and objective clinical evidence of 1 lesion 	
One of these criteria:
 
 • DIS: additional attack implicating different CNS site • DIS: ≥ 1 MS-typical symptomatic or asymptomatic T2 lesions in ≥ 2 areas of CNS: periventricular, juxtacortical/cortical, infratentorial or spinal cord 
AND
 
One of these criteria:
 
 • DIT: additional clinical attack • DIT: simultaneous presence of both enhancing and non-enhancing symptomatic or asymptomatic MS-typical MRI lesions • DIT: new T2 or enhancing MRI lesion compared to baseline scan (without regard to timing of baseline scan) • CSF-specific (i.e. not in serum) oligoclonal bands

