
To assess durability of clinical outcomes after treatment with IMP from Baseline (i.e. first dose^b of IMP) to Study Visit 1 in study participants previously treated with IMP as part of the Phase III ORACLE MS and CLARITY/CLARITY-EXT clinical trials.
	
Tertiary endpoints to be evaluated via retrospective data collection from medical records or at Study Visit 1:
 
 • Proportion of study participants being bedridden^d • Time from first dose^b of IMP to first use of an ambulatory device^d • Time from first dose^b of IMP to first use of a wheelchair^d • Annualized Relapse Rate (ARR) from time of first dose^b of IMP to Study Visit 1, and by 2-year intervals • Time to conversion to Clinically Definite MS (CDMS) (For ORACLE MS study participants only)

Exploratory Objectives	Endpoints (Outcome Measures)
	
 • Proportion of study participants diagnosed as Secondary Progressive MS (SPMS) without relapses in the 3 months prior to SPMS diagnosis • Proportion of study participants diagnosed as SPMS with relapses in the 3 months prior to SPMS diagnosis • Proportion of study participants diagnosed as Primary Progressive MS (PPMS) (For ORACLE MS study participants only)

To assess impact on quality of life and cognitive outcomes after treatment with IMP during the period from the last clinical visit in the CLARITY/CLARITY-EXT/ORACLE MS clinical trials to Study Visit 1 in study participants previously treated with IMP as part of the Phase III ORACLE MS and CLARITY/CLARITY-EXT clinical trials.
	
Tertiary endpoints to be evaluated at Study Visit 1:
 
 • Change in EuroQoL-5 Dimension Questionnaire (3 level version) (EQ-5D-3L) • Change in cognition as measured by the following assessments (to be collected for ORACLE MS subjects only in countries where these instruments were used in the CLASSIC MS study): 
 ○ The Brief Visuospatial Memory Test – Revised (BVMT-R) ○ Symbol Digit Modality Test (SDMT)

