Time-to-event data will be calculated from first dose of IMP in the parent study and will be presented using Kaplan-Meier estimates or cumulative incidence curves as appropriate. The analytical approach will be further detailed in the SAP.

Genetic variations will be analyzed descriptively. In addition, association of genetic variations with patients experiencing long-term response will be analyzed.

Adverse events will be summarized by number and frequency of patients with events.

Endpoint	Statistical Analysis Methods
Primary	Percentage and 95% CI
Secondary	Percentage and 95% CI
Tertiary/Exploratory	Descriptive statistics and time-to-event analyses as described above

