Cladribine high/placebo (HLPP): Subjects who were randomized to cladribine high dose with 1 or 2 cladribine 10 mg tablets per day over 4 to 5 days in Weeks 1, 5, 9, and 13 of Year 1, followed by Weeks 1 and 5 of Year 2 of the CLARITY study (25643) (total dose 5.25 mg/kg), and then to placebo for the years 1 and 2 of the CLARITY extension.

Cladribine low/placebo (LLPP): Subjects who were randomized to cladribine low dose with 1 or 2 cladribine 10 mg tablets per day over 4 to 5 days in Week 1 and Week 5 of Years 1 and 2 of the CLARITY study (25643) (total dose 3.5 mg/kg), then on placebo for the years 1 and 2 of the CLARITY extension study.

Placebo/Cladribine low dose (PPLL): Subjects who were randomized to placebo for the first and second year of CLARITY study (25643), then to cladribine low dose with 1 or 2 cladribine 10 mg tablets per day over 4 to 5 days in Week 1 and Week 5 of Years 1 and 2 of the CLARITY extension study.

Due to administrative reasons, there was a varying period (median time 41 weeks, range 1 day to 118 weeks) between a subject completing the CLARITY study and starting in the CLARITY EXT study, subjects did not receive cladribine during this time period. Following the end of the 96-week CLARITY EXT study period, subjects were followed for safety for an additional 24 weeks. The primary objective of this trial was to evaluate the safety of extended treatment with oral cladribine when administered to subjects who completed CLARITY (25643).

ORACLE MS (28821): The ORACLE MS (ORAl CLadribine in Early MS) study was a Phase III, randomized, double-blind study to evaluate the safety and efficacy of oral cladribine tablets as a monotherapy in subjects at risk of developing MS (subjects who have experienced a first clinical event suggestive of MS). Subjects were randomized to either oral cladribine high dose with 1 or 2 cladribine 10 mg tablets per day over 4 to 5 days in Weeks 1, 5, 9, and 13 of Year 1, followed by Weeks 1 and 5 of Year 2 (total dose 5.25 mg/kg), or oral cladribine low dose with 1 or 2 cladribine 10 mg tablets per day over 4 to 5 days in Week 1 and Week 5 of Years 1 and 2 (total dose 3.5 mg/kg), or matching placebo. The design was a time-to event design with treatment schedules dependent on conversion to clinically definite multiple sclerosis (CDMS) according to the Poser criteria at any time during the first 96 weeks:

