Subjects who converted to CDMS according to the Poser criteria at any time during the first 96 weeks (i.e., during the double-blind period) stopped the blinded study drug and entered an open-

label maintenance period, where they were offered open-label IFN- β and underwent evaluations for safety and efficacy.

All other subjects were planned to continue their blinded treatment up to the end of the first 96 weeks double-blind period (end of Year 2).

At the end of the first 96 weeks double-blind period, McDonald MS 2005 was assessed for all subjects and treatment schedules depended on the outcome:

- Subjects who converted to McDonald MS criteria were allocated to receive open-label oral cladribine (3.5 mg/kg) administered with 1 or 2 cladribine 10 mg tablets per day over 4 to 5 days in Week 1 and Week 5 of Years 1 and 2 (total dose 3.5 mg/kg) of the extension phase.
- Subjects who did not convert McDonald MS criteria at end of Week 96 were to be followed without treatment.
- At any time during the Extension phase, open-label cladribine with 1 or 2 cladribine 10 mg tablets per day over 4 to 5 days in Week 1 and Week 5 of Years 1 and 2 (total dose 3.5 mg/kg) if conversion to McDonald MS criteria or IFN- β (if conversion to CDMS) may have been used following the rule above.

The ORACLE MS was terminated earlier than planned in October 2011. No further dosing of blinded study medication or open-label cladribine was allowed (open-label IFN- β was offered for subjects who converted to McDonald MS). Subjects were to complete the end of trial visit assessments after a safety follow-up period of 24 weeks from the time of last dose of blinded study medication or open label cladribine.

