14.1 Primary Endpoint

The primary efficacy endpoint of this study will be evaluated descriptively by percentage and 95% CI of patients using a wheelchair most of the time ($EDSS \geq 7$) in the 3 months prior to Study Visit 1 or patients bedridden any time prior to visit 1. Forest plots will also be used to display these results.

In addition, analysis will be adjusted via logistic regression with parent studies (CLARITY or ORACLE), treatment group, and disease duration (at study visit 1) as continuous variable as factors for cohort A and with only disease duration (at study visit 1) as factors for cohort B, C and D. Estimate with likelihood based 95% CI within each parent study treatment group (exposed/not exposed) will be presented.

To identify the primary endpoint, the following source data used will be:

- Both AWB eCRF page and retro EDSS page will be considered. ($EDSS \geq 7$ in the 3 month prior to SV1 or $EDSS \geq 8$ after FDIMP)
- $EDSS \geq 7$ will also be considered (EDSS SV1).
- Participants who died due to MS are included in this proportion also (reason of death is MS disease related).

Disease duration = $(SV1 - \text{date of MS diagnosis} + 1) / 365.25$

Date of MS diagnosis is taken from CLARITY eCRF for CLARITY and CLARITY EXTENSION patients. For ORACLE MS patient, the MS diagnosis is the date of CDMS conversion collected either during the parent study or after the end of the parent study until SV1.

Logistic Regression:

The following SAS code will be used:

```
proc genmod data=sourcedata;
where avalc ne "U";
class STUDY TRT ;
model avalc = STUDY TRT DISEASE_DUR /dist=binomial link=logit lrci wald;
  Estimate "Never Exposed to Cladribine" intercept 1 Trt 1 0 / exp e;
  Estimate "Exposed to Cladribine" intercept 1 Trt 0 1 / exp e;
  Estimate "Never Exposed to Cladribine vs Exposed to Cladribine" Trt -1 1
/exp e;
  lsmeans trt / cl;
  ods output estimates=ESTIMATES lsmeans=lsmean; run;
```

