ARR from time of FDIMP to Study Visit 1 is calculated for each treatment group:

$$\text{ARR} = [(\text{sum of relapses} * 365.25) / (\text{sum of time on study in days until SV1})]$$

ARR from time of FDIMP to Study Visit 1 and by 2-year intervals is calculated for each treatment group:

$ARR = [(sum\ of\ relapses\ *365.25) / (sum\ of\ time\ on\ main\ study\ by\ 2\text{-}year\ intervals\ in\ days\ until\ SV1)]$

Time on study = Study Visit 1 – first dose of IMP +1

ARR from time of last dose of IMP to Study Visit 1 will be calculated similarly.

Table 5: Time window for ARR by 2-year intervals

Cumulative intervals	Time intervals
Less than 2 years	1 to 730 days
2 nd years to 4 th years	731 to 1461 days
4 th years to 6 th years	1462 to 2191 days
6 th years to 8 th years	2192 to 2922 days
X th years to Y th years...	Truncate (X*365.25 +1) to truncate (Y*365.25) days

Time to CDMS (Cohort D only)

Number of participants who converted to CDMS since first and last dose administered will be summarized descriptively.

Both information collected in “Conversion to CDMS” eCRF page and ORACLE MS parent study dataset will be used to identify participants who converted to CDMS after first/last dose of IMP.

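### Conversion to CDMS in ORACLE MS participants combines a Poser-based trial period with a McDonald 2017 follow-up period, so the tertiary endpoint has no single event definition

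*Protocol*

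**What the plan says.** The endpoint is listed in the Protocol synopsis as "Time to conversion to Clinically Definite MS (CDMS) (For ORACLE MS study participants only", under the tertiary objective on durability of clinical outcomes. Protocol 9.4 sets the time origin: "Time-to-event data will be calculated from first dose of IMP in the parent study". Follow-up therefore runs through ORACLE MS and the years after it.

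Three passages bear on the event definition:

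- **During ORACLE MS.** SAP 6.2 describes "treatment schedules dependent on conversion to clinically definite multiple sclerosis (CDMS) according to the Poser criteria at any time during the first 96 weeks". It keeps a second outcome apart: "At the end of the first 96 weeks double-blind period, McDonald MS 2005 was assessed for all subjects". The two had different consequences. CDMS converters were offered open-label interferon beta, whereas McDonald converters were allocated open-label cladribine.
- **In CLASSIC-MS.** Protocol 8.1.1.8: "Conversion to CDMS will be determined according to the McDonald 2017 criteria", with the diagnostic table reproduced as Table 2 and in Appendix 6.
- **In the analysis.** SAP 14.3.2 says that the CLASSIC-MS conversion eCRF page and the "ORACLE MS parent study dataset will be used to identify participants who converted to CDMS after first/last dose of IMP".

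The same date has a second use. In SAP 14.1, "For ORACLE MS patient, the MS diagnosis is the date of CDMS conversion collected either during the parent study or after" its end, up to Study Visit 1. That date sets disease duration, a covariate in the adjusted logistic regression for the primary endpoint. SAP 7 records no change from the protocol analyses and does not mention the criteria.

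**The concern.** A time-to-event endpoint, or a proportion converted, needs one event. Here the part contributed by the parent trial and the part contributed by chart review and Study Visit 1 appear to follow different rules, and the later rule can be met without a second attack. A participant with one attack and supportive imaging or CSF could be unconverted under Poser when ORACLE MS closed and a CDMS converter under Protocol 8.1.1.8, with no relapse in between.

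The reported proportion and time would then mix clinical conversions with reclassifications, and a reader could not separate them. SAP 14 presents results by exposed and never-exposed groups, so any imbalance in the mix would also affect that contrast. Through SAP 14.1, the choice of criterion also influences disease duration for ORACLE MS participants.

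**Working it through.** No planned figure depends on this point. The documents give no event count, conversion rate or precision for CDMS, so the check is a comparison of texts, followed by an illustration on assumed values.

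**Step 1: set the definitions side by side.**

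| Period | Outcome called CDMS | McDonald outcome | Source |
|---|---|---|---|
| ORACLE MS | Poser | McDonald 2005, separate outcome | SAP 6.2 |
| After ORACLE MS, to Study Visit 1 | McDonald 2017 | Same thing | Protocol 8.1.1.8 |
| Analysis from first dose | Both sources combined | Not separated | SAP 14.3.2 |

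**Step 2: can McDonald 2017 be met without a new attack?** Protocol Table 2 has two one-attack rows. With objective evidence of two or more lesions, dissemination in time suffices. It can be shown by enhancing and non-enhancing lesions together or by a new T2 or enhancing lesion, and CSF-specific oligoclonal bands also count. With evidence of one lesion, dissemination in space is needed as well, and MRI can show that too. So the table allows attack-free conversion. How often it occurs cannot be learned from the documents.

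**Step 3: is the Poser side different?** The documents do not print the Poser criteria. The internal support is that ORACLE MS treated McDonald conversion as distinct from CDMS, with its own treatment path (SAP 6.2), and that Protocol 2.2 characterises the early-disease setting by the time to a second event.

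**Step 4: could the effect on the group contrast be signed?** Let c be the share converted by Poser at the end of ORACLE MS, and q the share of the unconverted who meet McDonald 2017 on one attack. Apparent conversion is c + (1 − c) × q, and the amount added by the definition is (1 − c) × q. Every value below is assumed: c = 15% exposed and 35% never exposed, a difference of 20 points and a ratio of 15/35 = 0.43.

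| q exposed / never exposed | Exposed | Never exposed | Difference (points) | Ratio |
|---|---|---|---|---|
| 0% / 0% | 15.0% | 35.0% | 20.0 | 0.43 |
| 30% / 30% | 15 + 0.85 × 30 = 40.5% | 35 + 0.65 × 30 = 54.5% | 14.0 | 0.74 |
| 30% / 50% | 40.5% | 35 + 0.65 × 50 = 67.5% | 27.0 | 0.60 |
| 50% / 30% | 15 + 0.85 × 50 = 57.5% | 54.5% | −3.0 | 1.06 |

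The amounts added are equal when 0.85 × q(exposed) = 0.65 × q(never exposed), that is, when the q ratio is 0.65/0.85 = 0.76. Below that the difference widens; above it the difference shrinks. For the conversion ratio, the break-even q ratio is 0.43 × 0.76 = 0.33.

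**Step 5: do the documents place q on one side?** They point both ways. Protocol 2.2 reports fewer new or enlarging T2 lesions on cladribine, which suggests a lower q in the exposed. SAP 6.2 and 8.2.1 together mean that a placebo patient who met McDonald 2005 and received open-label cladribine counts as exposed. This moves McDonald-positive patients out of the never-exposed group and suggests a higher q in the exposed. Early termination of ORACLE MS limited how many were dosed. The sign stays open.

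**The case against.** Protocol 8.1.1.8 gives no start date for McDonald 2017; read alone, it could govern the whole follow-up. The Poser component enters only because SAP 14.3.2 draws on the ORACLE MS dataset, and it does not say whether Poser CDMS or McDonald 2005 is taken. The eCRF page, which might record the criterion met, is not available. This stands as a limit on wording: what is shown is an unnamed source variable and a missing harmonisation rule, not a stated intention to switch criteria. It does not remove the problem. Under the parent trial's meaning of CDMS the two sources differ, and even if McDonald 2005 were taken, the versions would differ.

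A reader might infer more, and three such inferences fail:

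- *That the plan manufactures conversions at chart review.* Table 2 permits attack-free conversion; it does not produce it. Nor does any passage date the event at abstraction. Criteria met on old scans could carry an earlier date.
- *That the distortion is larger in the group with fewer Poser conversions.* This needs q to be about equal in both groups, and Step 5 gives no basis for that.
- *That disease duration should use an attack-only date.* Participants diagnosed without a second attack would then have no diagnosis date and would drop out of the regression in SAP 14.1. Those lost would be the relapse-free ones. For a covariate meaning time since MS diagnosis, a McDonald date is defensible.

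The impact is also narrow. The endpoint is tertiary and summarised descriptively, no hypothesis is tested, and SAP Appendix 17.1 lists Kaplan-Meier output only for ambulatory device and wheelchair. The main primary-endpoint result is an unadjusted percentage; the regression is additional.

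**Conclusion.** The point holds as a defect of definition. Followed as written, the plan gives Cohort D a conversion endpoint in which on-trial and post-trial events need not be the same kind of event. Neither the proportion nor the time to CDMS can then be interpreted without knowing the mix. This rests on reading the ORACLE MS conversion data as Poser-based, which is how SAP 6.2 defines CDMS there.

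Its size is unknown. The illustration shows only that the contrast between groups could shrink, widen or reverse under values the documents neither support nor exclude. No magnitude and no direction should be attributed to the study on this basis. The route through disease duration is real but unquantified, and it affects only the adjusted primary analysis. The matter should be settled before database lock, but it does not threaten the main primary result.

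**What to change.** In SAP 14.3.2, name the ORACLE MS source variable and replace the combined endpoint with two, each over the whole follow-up from first dose:

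1. **Attack-based conversion.** Use the Poser CDMS date on trial. After the trial, for those not yet converted, use the first relapse onset date from the relapse module (Protocol 8.1.1.7). Describe the post-trial part as an approximation to Poser.
2. **McDonald conversion.** State the version that applies in each period: 2005 in ORACLE MS and 2017 in CLASSIC-MS.

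In SAP 14.1, state which diagnosis date defines disease duration for ORACLE MS participants. Do not substitute the attack-only date in the main model; add a sensitivity analysis with the alternative date and report how many participants lack a value under each.

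The cost is protocol and SAP wording, one derivation and a few extra table rows, using fields the protocol already calls for. The downside is that chart relapses are recorded only where available and are less well documented than on-trial events, so attack-based conversion may be under-counted after the trial. That limitation should be reported with the result.
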